9.6 POWER AND SAMPLE SIZE JUSTIFICATION

The sample size of approximately 190 per treatment arm (380 total) will provide approximately 82% power to establish the non-inferiority with a 13.5% non-inferiority margin for the primary efficacy variable, RR Weeks 2-25. In the sample size calculation, it was assumed that the proportion of response in both the active treatment arm and control treatment arm is 70%.

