12.3.2. Analysis of Efficacy Measures

12.3.2.1. Analysis of the Primary Efficacy Endpoint

The responder definition will be derived based on urine samples obtained from Weeks 10, 11, 12 and 13 in Phase 1 and samples obtained at Weeks 17 (Month 1), 21 (Month 2) and 25 (Month 3) and at the 3 random samples in Phase 2.

To be a responder for Phase 1, the subject must have no evidence of illicit opioids use at Week 13 and have no evidence of illicit opioids use for at least 2 out of the three weeks from Week 10 to Week 12. To be a responder for Phase 2, the subject must have no evidence of illicit opioids use at Month 6 (last illicit opioids use assessment in Month 6 or Week 25) and have no evidence of illicit opioids use in 5 out of the 6 illicit opioids use assessments in Phase 2. To be a responder for the study, the subject must be a responder for both Phases 1 and 2. Evidence of illicit opioid use is defined as a positive opioid urine toxicology result or a self-reported illicit opioid use.

The primary efficacy variable will be RR. The proportion of responders will be calculated in both treatment arms.

An analysis of non-inferiority in the primary efficacy variable between the two treatments arms will be performed using a margin of 13.5% point.

Non-inferiority will be concluded if the two-sided 95% confidence interval for the difference between the probabilities of response (Active- Control) is above -0.135 . The 95% confidence interval, (LB, UB), will be derived using normal approximation:

$$LB = (P_T - P_C) - 1.96 * (1/N_T * P_T * (1 - P_T) + 1/N_C * P_C * (1 - P_C))^{0.5}, \text{ and}$$
$$UB = (P_T - P_C) + 1.96 * (1/N_T * P_T * (1 - P_T) + 1/N_C * P_C * (1 - P_C))^{0.5}, \text{ where}$$

P_T and P_C are observed proportions of the responders for the treatment and the control, respectively, and N_T and N_C are the sample sizes for the treatment and the control, respectively.

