12.5. Determination of Sample Size

The primary efficacy variable is based on data from Week 2 to Week 25. Approximately 380 subjects (190 subjects per arm) will be randomized.

The sample size of 190 subjects per treatment arm (380 total) was selected to achieve approximately 82% power to establish non-inferiority based on the primary efficacy variable, RR (Week 12-25). In the sample size calculation, it is assumed that both arms have a 70% RR, and that the non-inferiority margin is 13.5%.

Choice of non-inferiority margin for the primary endpoint

The proposed 13.5% margin is appropriate from a scientific validity perspective as well as meeting the FDA guidelines for non-inferiority selection (24). The FDA draft guidance on non-inferiority trials suggest 50% of the benefit of the control arm relative to a placebo or no care would be a reasonable approach. The following information provides additional credence to the rationale:

1. In the study by Rosenthal et al (27), the RR between open-label SL BPN/naloxone and placebo was found to be approximately 33% and 6%, a difference of 27% (lower limit of a two-sided confidence interval for the difference; 17%, using an approximate 95% confidence level) over 24 weeks of treatment (data derived from Fig 2 in Rosenthal et al). The expectation, based on this, is that a hypothetical placebo arm in this trial, HS-11-421, would be worse than the SL BPN control arm by at least a 17% difference in RR. Note that using the suggested 50% of the benefit of the control arm in this trial will imply a non-inferiority margin of 13.5%. Thus, using 13.5% as the non-inferiority margin should be viewed as conservative as the lower limit of the associated confidence interval for the difference is 17%.
2. In addition, the FDA Draft Guidance (24) notes that circumstances might support a conservative choice for the margin, including:
 - a. *Pharmacologic properties of the test drug that are very similar to those of the active control* – CAM2038 is an alternative dosage form of the same active entity with the expectation of similar overall average plasma concentrations to the SL BPN arm;
 - b. *Use of a persuasive biomarker* – responder definition in this trial will include the standard and well-accepted objective urine toxicology results to confirm treatment success with with respect to drug use;

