3.0 INTRODUCTION

This statistical analysis plan (SAP) is based on Protocol HS-11-421 Amendment 5, dated on November 3, 2016.

The purpose of this document is to provide details on study populations and on how the variables will be derived, how missing data will be handled, as well as details on statistical methodologies to be used to analyze the safety and efficacy data from the study.

The document may evolve over time, for example, to reflect the requirements of protocol amendments or regulatory requests. However, the final SAP must be finalized, approved by the Sponsor, and placed on file before database is locked and treatment codes are unblinded. Deviations from the approved plan will be noted in the clinical study report.

The primary endpoint response rate will be used to address the regulatory requirements as outlined by the US Food and Drug Administration (FDA). Specifically, the FDA requested an alternative primary efficacy responder definition on September 1, 2016, which have been incorporated in this final SAP. Additionally, the FDA provided comments on November 4, 2016 and recommended a NI margin of 10% points to be reasonable NI margin for the study. This change is reflected in this final SAP.

The European Medical Agency (EMA) has requested percent negative urine samples as the primary endpoint and retention rate as key secondary endpoint. These requests are addressed in a separate SAP for EMA submission. The variables related to the percentage of urine sample negative (EMA specific variables) are removed from Version 1.01 that is for FDA submission.

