9.1.2 PRIMARY ANALYSIS

The primary analysis of RR will be performed based on the ITT population.

An analysis of non-inferiority in the primary efficacy variable between the two treatments arms will be performed using a margin of 10% point.

Non-inferiority will be concluded if the two-sided 95% confidence interval for the difference between the probabilities of response (Active- Control) is above -0.10 . The 95% confidence interval, (LB, UB), will be derived using normal approximation:

$$\text{LB} = (P_T - P_C) - 1.96 * (1/N_T * P_T * (1 - P_T) + 1/N_C * P_C * (1 - P_C))^{0.5}, \text{ and}$$
$$\text{UB} = (P_T - P_C) + 1.96 * (1/N_T * P_T * (1 - P_T) + 1/N_C * P_C * (1 - P_C))^{0.5}, \text{ where}$$

P_T and P_C are observed proportions of the responders for the treatment and the control, respectively, and N_T and N_C are the sample sizes for the treatment and the control, respectively.

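### The SAP tests non-inferiority at a 10-point margin but still quotes 82% power at 13.5 points; at 10 points power is about 57%, and the protocol still decides at 13.5

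*SAP*

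**What the plan says.** **SAP.** Section 3.0 records that on 4 November 2016 the FDA "recommended a NI margin of 10% points to be reasonable NI margin for the study", and states that the final SAP carries this change. Section 9.1.2 puts it into the decision rule: the comparison "between the two treatments arms will be performed using a margin of 10% point", and success requires the two-sided 95% interval for active minus control to lie above -0.10. Section 9.6 gives the only power statement for the primary endpoint: "approximately 82% power to establish the non-inferiority with a 13.5% non-inferiority margin for the primary efficacy variable, RR Weeks 2-25", with about 190 per arm and 70% response assumed in both arms. The SAP gives no power at 10 points.

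**Protocol.** Section 12.3.2.1 says that the non-inferiority analysis "will be performed using a margin of 13.5% point", with success if the interval is above -0.135. The synopsis repeats this. Section 12.5 uses 13.5 points for the sample size and argues for that margin as half of a 27-point historical difference.

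**Endpoint window.** The power text labels the responder rate as Weeks 2-25 (SAP 9.6, protocol synopsis). Protocol 12.5 gives both Week 2 to Week 25 and Week 12-25. The responder definition in SAP 9.1 and protocol 12.3.2.1 uses Weeks 10 to 13 plus the six Phase 2 assessments.

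**The concern.** A power statement should describe the test that will decide the trial. Here the margin was tightened by 3.5 points while the sample size, the assumed response rates and the quoted power all stayed the same. That cannot be right, because a tighter margin with everything else fixed lowers power. A reader of SAP 9.6 would overestimate the chance that the primary test succeeds when the two arms are truly equal.

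The second problem is the success criterion itself. As the texts stand, a lower confidence limit between -13.5 and -10 points meets the protocol's rule and fails the SAP's. If such a result appeared after unblinding, there would be a dispute over which threshold had been pre-specified for the primary endpoint.

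**Working it through.** **Inputs**

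- 190 per arm, 1:1 allocation (SAP 9.6, 4.3).
- Response 70% in both arms, so the true difference is 0 (SAP 9.6).
- Two-sided 95% interval, unpooled normal approximation, multiplier 1.96 (SAP 9.1.2), no continuity correction (SAP 6.0).
- No allowance for dropout is needed: SAP 9.1.3 imputes every missing urine sample as positive, so all randomized subjects count.
- Margins: 0.135 (SAP 9.6 and protocol) and 0.10 (SAP 9.1.2).

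**Formula**

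SE = sqrt(2 × 0.7 × 0.3 / 190) = 0.0470

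Power = Φ(margin / SE − 1.96)

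**Step 1: reproduce the plan's figure.** At 0.135: Φ(2.871 − 1.96) = Φ(0.911) = 81.9%. This matches the stated 82%. Solving the other way, 82% power needs 191 per arm, against 190 planned.

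**Step 2: use the margin in the decision rule.** At 0.10: Φ(2.127 − 1.96) = Φ(0.167) = 56.6%.

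**Step 3: check without the approximation to power.** Enumerating all binomial outcomes and applying the SAP's interval rule to each gives 81.9% at 13.5 points and 56.8% at 10.

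**Step 4: size of the disputed zone.** 81.9% − 56.6% = 25.3% of trials would have a lower limit between -13.5 and -10. In observed terms, the half-width near 70% response is 1.96 × 0.0470 = 9.2 points. The trial therefore passes at 13.5 with an observed difference better than about -4.3 points, but at 10 it needs better than about -0.8.

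**Step 5: other common response rates.** Same formula, 190 per arm. Rates other than 70% are assumptions. The 33% is the sublingual buprenorphine/naloxone figure that protocol 12.5 takes from its cited historical trial.

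| Response, both arms | Power at 10 points | Power at 13.5 points | Gap |
|---|---|---|---|
| 70% | 56.6% | 81.9% | 25.3 |
| 60% or 40% | 51.2% | 76.6% | 25.4 |
| 50% | 49.6% | 74.9% | 25.3 |
| 33% | 54.5% | 79.9% | 25.4 |
| 20% | 68.3% | 90.8% | 22.5 |
| 15% | 77.9% | 95.8% | 17.9 |

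No rate in the table reaches 82% at 10 points. Power passes 82% only at lower rates still (90.1% at 10% response).

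**Step 6: other conventions at 10 points, 70% response.** One-sided 0.05 gives 68.5%, a continuity correction 52.2%, and pooled variance 53.3%. None recovers 82%.

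**Step 7: sample size, for reference only.** For 82% power at 10 points: (1.96 + 0.915)² × 0.42 / 0.01 = 347.2, so 348 per arm. For 80% it is 330 per arm, and for 90% it is 442.

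**The case against.** The best defence has four parts.

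1. SAP 9.6 contains no miscalculation. It names its margin, rate and sample size, and 82% is right for them. This stands: the fault is an outdated justification. But the section exists to justify the sample size for the planned primary test, and that test uses 10 points.

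2. The SAP governs. Protocol 12.1 allows the SAP to amend the listed analyses. The SAP is based on Amendment 5 of 3 November 2016, one day before the FDA comment, and it openly explains the change. On that reading, a lower limit between -13.5 and -10 is a failure. This explains why the protocol lags and gives a good argument for which rule prevails. It leaves two different thresholds in the current texts, and it does not touch the conflict inside the SAP between 9.1.2 and 9.6.

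3. The 57% depends on 70% response. Missing samples count as positive and response is required in both phases, so the true rate may differ. The historical 33% comes from an open-label arm of another trial, and the documents do not show that its responder definition matches this one. All this is fair, and the 25% figure also falls to about 18% at 15% response. But 70% is the plan's own assumption, and power stays below 82% across the whole 15% to 70% range.

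4. The window label is part of a wider inconsistency. SAP 9.5 also says Weeks 2-25, and SAP 9.1.1 bases Phase 1 response on the Week 2-13 samples. This is correct. The label does not enter the power arithmetic, and relabelling the power text alone would leave 9.1.1 to be reconciled with 9.1.

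**Conclusion.** The concern holds. The quoted 82% is not the power of the primary test in the SAP. With 190 per arm, 70% response in both arms and the SAP's own interval, power at the 10-point margin is 56.6% (56.8% by enumeration). The chance of missing non-inferiority with truly equal arms is therefore about 43%, where the text implies about 18%. Separately, the protocol and SAP state different success thresholds for the primary endpoint, and on the same assumptions about one trial in four would fall between them. The exact figures depend on the assumed response rate; the conclusion does not, for any common rate from 15% to 70%. This must be corrected before unblinding, because it concerns the primary success criterion.

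**What to change.** - **One threshold.** Amend the protocol synopsis, 12.3.2.1 and 12.5 to the SAP's 10-point margin. The margin argument in 12.5 is built to arrive at 13.5 (half of 27), so it must be rewritten to support 10 and not merely renumbered.
- **Power.** In SAP 9.6 and protocol 12.5 (and the matching synopsis text), replace the 82% statement with: about 57% power at a 10-point margin, 190 per arm, 70% response in both arms. Add a short table of power for response rates from 15% to 70%, with the rates labelled as assumptions.
- **Window.** Label the endpoint with the samples it uses (Weeks 10-25), and reconcile the Weeks 2-13 wording in SAP 9.1.1 and the Weeks 2-25 label in SAP 9.5 at the same time.

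No change in sample size is proposed. The cost is text in both documents and a less favourable stated power. The protocol part is an amendment under section 13.6, so it needs IRB approval unless it qualifies as administrative. The SAP part can be done at once.

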10.0 SUMMARIES OF MEASURES OF SAFETY

Safety analyses will be performed for the safety population. Safety evaluations will be based on the incidence, intensity, and type of adverse events (AEs), as well as on clinically significant changes in the subject's physical examination, vital signs, and clinical laboratory results, Injection site examination and wound care. Safety variables will be tabulated and presented by study drug actually received.

Because there is no pre-specified safety outcome defined in terms of AEs, clinically relevant laboratory parameters, or vital signs, any formal comparisons between the treatment arms with respect to specific safety parameters will be post-hoc.

10.1 EXTENT OF EXPOSURE

Summary statistics (number and percentage) of weeks of exposure to study drug (i.e. from date of initial injection to 4 weeks after the last injection) will be tabulated by treatment group.

10.2 ADVERSE EVENTS

Each AE and serious adverse event (SAE) term recorded on the CRFs will be mapped to a primary system organ class (SOC) and a preferred term using the MedDRA dictionary. The investigator will assess AE severity and relationship to the study treatment.

Columbia Suicide Severity Rating Scale (C-SSRS) will be summarized.

A treatment-emergent adverse event (TEAE) is defined as any AE with an onset date on or after date of randomization, or any ongoing event on the date of first dose that worsens in severity after date of randomization. Only TEAEs with an onset date prior to date of last dose + 30 days will be tabulated in

summary tables. For the purpose calculating treatment emergence and inclusion in summary tables, incomplete onset dates will be imputed as detailed in Appendix A.

TEAEs will be summarized by the number and percent of subjects in each primary SOC and preferred term. Patients will be counted only once for each primary SOC and each preferred term. Summary tables of TEAEs by primary SOC, preferred term and intensity will be provided. If a subject has more than one AE coded to the same preferred term, the subject will be counted only once for that preferred term by using the event with the highest intensity. Similarly, if a subject has more than one AE within a primary SOC category, the subject will be counted only once in that SOC category by using the event with the highest intensity. AEs by primary SOC, preferred term and relationship to study drug will be provided as well. If a subject has more than one AE coded to the same preferred term, the subject will be counted only once for that preferred term by using the most related event. Similarly, if a subject has more than one AE within a primary SOC category, the subject will be counted only once in that primary SOC category by using the most related event. In addition, SAEs by primary SOC and preferred term will be provided. Deaths and SAEs will be summarized similarly to AEs. All TEAE tables will also include the total number of events, counting multiple events per patient.

Injection related AEs, other (non-injection related) AEs as well as all AEs will be presented by treatment group and overall. Summaries of these AE subsets will be presented for the following categories:

- Study drug related
- Intensity
- Relationship to injection
- Possibly study drug related by intensity
- Reasonably injection related by intensity
- Serious
- AEs which led to discontinuation of treatment
- SAEs which led to discontinuation of treatment
- AEs occurring in 5% or greater of any treatment group (by preferred term)

In the AE summary, preferred terms within each SOC will appear in alphabetical order.

Frequencies for deaths and hospitalizations will also be summarized by treatment group and overall.

To assess the AE profile during the first week of treatment (first week after the randomization), TEAEs that occur within the first week of treatment will be presented.

Other safety analyses will be performed as appropriate

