7.1.3. Phase 2 (Monthly Visits)

Weeks 13 to 24:

At Week 13 visit, all subjects will be transitioned to monthly treatment (dispensing for SL BPN/Placebo or SC injections). Before transitioning to CAM2038 q4w, subjects will be evaluated for the stability criteria described above.

Treatment: Subjects will receive the following treatments for a duration of 12 weeks:

- Group 1 (SL BPN): daily SL BPN + injections of once monthly SC placebo
- Group 2 (CAM2038): injections of once monthly CAM2038 q4w SC + daily SL placebo

Subjects will therefore receive their first dose of CAM2038 q4w (or placebo) at the beginning of Week 13 (± 2 days), preferably Monday. Subjects will receive their monthly SL tablets (SL BPN or placebo) and an SC injection (CAM2038 q4w or placebo) while on site.

Subjects will continue to receive the daily dose of SL BPN or SL placebo that they received at the end of Phase 1. Based on their CAM2038 q1w (or SC placebo) dose at the end of Phase 1, subjects will be transitioned to the following doses of CAM2038 q4w or placebo SC injection in Phase 2:

- 16 mg CAM2038 q1w/placebo = 64 mg CAM2038 q4w/placebo
- 24 mg CAM2038 q1w/placebo = 96 mg CAM2038 q4w/placebo
- 32 mg CAM2038 q1w/placebo = 128 mg CAM2038 q4w/placebo

Dosage adjustment will be allowed during Phase 2 at the monthly scheduled visits only, up to a maximum of 32 mg SL BPN (or placebo) and up to 160 mg CAM2038 q4w (or placebo), as outlined in Section 9.1.2.

Subjects will return to the clinic for monthly trial visits during Phase 2. In addition to the monthly visits, subjects will return to the clinic to provide 3 random urine toxicology samples during Phase 2 of the trial. At each scheduled monthly visit, SL tablets (BPN or placebo) sufficient to last until the next visit will be dispensed. Subjects will also receive SC injections on site at the Week 13 (± 2 days), 17 and 21 visits (± 7 days). Urine toxicology samples will be taken at each scheduled or random visit for illicit testing of opiates/opioids and self-reports of illicit drug use will be collected in connection to the urine samplings. Other drugs of abuse will also be assessed. During Phase 2, a total of 6 urine toxicology samples will be collected; 3 at scheduled visits (1 per month) and 3 at random urine toxicology visits. COWS/SOWS and VAS will be performed at each scheduled trial visit. Other outcome measures and safety assessments are outlined in Table 4.

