9.7. Prior and Concomitant Therapy

All non-trial medications, including prescription, over-the-counter, or herbal therapies, used by the subject will be documented for the 30 days prior to Screening and throughout the trial. The Investigator will determine if the prior/concomitant medication(s) affect the subject's eligibility to participate or continue to participate in the trial. The following restrictions on concomitant medications will be in place during the trial:

- Opioid receptors are likely to be occupied by BPN, which may reduce the analgesic effects of an opioid. The dissociation of BPN from the receptors may take several days following discontinuation of SL BPN treatment, or up to 2 weeks (for CAM2038 q1w) or at least 2 months (for CAM2038 q4w) following the last CAM2038 injection. Therefore, subjects requiring analgesic emergency treatment or anesthesia for surgery should ideally be treated with a non-opioid analgesic. Opioids may be used with caution, but as higher doses may be required for analgesic effect, there may be a higher potential for toxicity with opioid administration. The clinical course should carefully evaluated and be fully documented for subjects who have a requirement for any opioid analgesic for >7 days continually or general anesthesia for surgery.
- BPN is metabolized via CYP3A4. Because CYP3A4 inhibitors may increase plasma concentrations of BPN, if CYP3A4 inhibitors such as azole antifungals (e.g., ketoconazole), macrolide antibiotics (e.g., erythromycin), and HIV protease inhibitors (e.g., ritonavir, indinavir, and saquinavir) are required, the Medical Monitor must be consulted. Interactions with CYP 3A4 inducers have not been investigated; therefore it is recommended that the use of agents such as phenobarbital, carbamazepine, phenytoin and rifampicin be avoided in subjects receiving trial treatment. The Medical Monitor must be consulted prior to starting subjects on any of these agents.

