Abbreviations: BMI=body mass index; BPN=buprenorphine; COWS=Clinical Opiate Withdrawal Scale; C-SSRS=Columbia Suicide Severity Rating Scale; ECG=electrocardiogram; M=month; SC=subcutaneous; SL=sublingual; SOWS=Subjective Opiate Withdrawal Scale; VAS=visual analogue scale; W=week.

^h Subjects will receive the first CAM2038 q4w injection (active or placebo) at the beginning of Week 13 (±2 days). Not to exceed 160 mg CAM2038 q4w (or placebo) per month. Subjects will receive their last CAM2038 q4w dose at Week 21.

ⁱ Any spontaneously reported adverse events will be recorded after the subject signs the informed consent form. In addition, adverse events will be elicited using a non-leading question each time the subject visits the clinic and during the telephone contacts in the Follow-up phase.

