10.4.1.1. Adverse Event Reporting

All AEs must be entered on the AE CRF, regardless of causality or severity. AEs include new AEs, worsening baseline conditions, clinically significant laboratory findings, disease-related signs and symptoms that were not present at baseline, and any events or findings that the Investigator considers clinically significant.

Disease-related signs and symptoms that are present at baseline should not be recorded as AEs unless they worsen in severity or increase in frequency.

Information collected concerning AEs will include the following:

- Name of the event
- Onset date
- Resolution date
- Severity (i.e., mild, moderate, or severe)
- Relationship to trial drug
- Action and outcome
- Seriousness of event

All AEs will be documented and followed from the time the subject has signed the ICF until 14 days after the Follow-up Visit at Week 29 or early termination. SAEs and AEs that have been designated as related to trial drug will be followed until resolution or stabilization.

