5.0 ANALYSIS POPULATIONS

5.1 SAFETY POPULATION

The safety population will include all subjects who have any dose of SL BPN/placebo or SC CAM2038/placebo injection. Analyses based on this population will group subjects according to the treatment they actually received regardless of the treatment they were randomized to receive. All safety analyses will use the safety population.

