8.0 PRIOR AND CONCOMITANT MEDICATIONS

All medications recorded on the CRFs will be coded using the WHO DRUG Dictionary Enhanced March 2015. Prior and concomitant medications will be summarized by treatment arm in the safety population by anatomical therapeutic chemical Class Level 4 and WHO Drug base substance preferred name.

Prior medications are defined as medications with stop dates occurring before the date of first administration of any study treatment component. Concomitant medications are defined as medications with start dates occurring on or after the date of first administration of any study treatment component and no more than 30 days after the last administration of any study treatment component. Medications

with start and stop dates that bracket the date of first administration of any study treatment component will be summarized as both prior and concomitant medications.

Medications that clearly stopped prior to date of first administration of any study treatment component will be included in the prior medications table, and medications that clearly started on or after date of first administration of any study treatment component will be included in the concomitant medications table. All other medications will be included in both the prior and concomitant medications tables.

Prior and concomitant medication will be summarized for the safety population.

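### SAP 10.2 cuts the AE summary tables at last dose + 30 days without saying which dose, so collected follow-up events go untabulated: 14 or 41 days for an on-schedule completer

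*SAP*

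**What the plan says.** SAP 10.2 counts an AE as treatment-emergent from randomization, then limits the summary tables: "Only TEAEs with an onset date prior to date of last dose + 30 days will be tabulated". It adds that deaths and SAEs are summarized in a similar way. Protocol 12.4, which describes the AE summaries, contains no such limit.

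The AE rule does not define last dose, and the SAP uses different anchors elsewhere:

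- SAP 5.1 counts a tablet or an injection as a dose: "all subjects who have any dose of SL BPN/placebo or SC CAM2038/placebo injection".
- SAP 8.0 limits concomitant medications to "no more than 30 days after the last administration of any study treatment component".
- SAP 10.1 measures exposure from injections only, ending 4 weeks after the last one.

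The design is double-dummy, so both arms take tablets and injections. On injections, Protocol Table 4 says: "Subjects will receive their last CAM2038 q4w dose at Week 21". On tablets, Protocol 7.1.3 says that at each monthly visit "SL tablets (BPN or placebo) sufficient to last until the next visit will be dispensed", so daily tablets continue to about Week 25.

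Protocol 10.4.1.1 has AEs followed "until 14 days after the Follow-up Visit at Week 29 or early termination". Protocol 8.3 asks sites to keep collecting AEs in subjects who stop trial drug, unless consent is withdrawn. Protocol 9.7 says that dissociation from the receptors may take several days after SL BPN, up to 2 weeks after the weekly depot, "or at least 2 months (for CAM2038 q4w) following the last CAM2038 injection".

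**The concern.** Two programmers could follow SAP 10.2 faithfully and produce different AE tables, because the last tablet and the last injection fall about four weeks apart. Under either choice the tables stop before AE collection does for an on-schedule completer, so some events that sites were asked to record never enter a by-arm incidence table of TEAEs.

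The single 30-day window also sits beside the protocol's own statement that persistence differs by product, and is longest for the monthly depot, which only the CAM2038 arm receives. At stake is how completely late events after the depot are summarized by arm, including SAEs if their tables inherit the same limit. No efficacy conclusion is affected.

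**Working it through.** **Calendar.** Protocol 7.1.2 places Day 8 at Week 2, so the Week w visit is Day 7(w − 1) + 1:

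- Week 21 = 7 × 20 + 1 = Day 141
- Week 25 = 7 × 24 + 1 = Day 169
- Week 29 = 7 × 28 + 1 = Day 197

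Check against the plan's own figures in Protocol 7.1: 3 screening weeks + (197 − 1)/7 = 31 weeks in the trial, and (169 − 1)/7 = 24 weeks of treatment. Both match. SAP 9.2.2 instead labels Week 25 as Day 175. That shifts each of these days by 6 and leaves the gaps unchanged.

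**Inputs for an on-schedule completer**

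- Last q4w injection: Day 141 (Table 4).
- Last tablet: about Day 168, the day before the Week 25 visit (from Protocol 7.1.3).
- End of AE collection: 197 + 14 = Day 211.
- Last tabulated day: last dose + 29, because onset must fall before last dose + 30.
- Depot period: last injection + 60 days. The 60 is an assumption for 2 months; 56 and 61 are also shown. The protocol says at least, so the period could be longer.

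| | Last dose = injection | Last dose = later of tablet and injection |
|---|---|---|
| Last dose | Day 141 | Day 168 |
| Last tabulated day | 141 + 29 = 170 | 168 + 29 = 197 |
| Days after last injection covered | 29 | 197 − 141 = 56 |
| Collected days untabulated | 211 − 170 = 41 | 211 − 197 = 14 |
| Depot days untabulated, 60-day period (to Day 201) | 201 − 170 = 31 | 201 − 197 = 4 |
| Same, 56 days (to Day 197) | 27 | 0 |
| Same, 61 days (to Day 202) | 32 | 5 |

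**Visit windows.** Weeks 21 and 25 each allow ±7 days. Under the tablet-or-injection reading with a 60-day period, the depot gap then ranges from 0 to 18 days. The largest gap arises with Week 21 a week late and Week 25 a week early: injection Day 148, depot end Day 208, last tablet Day 161, tables end Day 190, and 208 − 190 = 18.

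**Subjects who stop early.** Suppose a subject stops tablets t days after the last q4w injection and stays in follow-up. Under the tablet-or-injection reading the untabulated depot days are 60 − (t + 29) = 31 − t: 31 at t = 0, 17 at t = 14, 3 at t = 28. If Protocol 10.4.1.1 is read as ending AE collection 14 days after early termination, fewer events are collected after the cut and this gap shrinks.

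**The case against.** A reader might infer that the SAP simply discards the second month of depot exposure and so flatters the test arm. The documents do not support that, for these reasons:

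- **The natural reading is the wider one.** SAP 5.1 and the parallel 30-day rule in SAP 8.0 both count tablets. On that basis an on-schedule completer is covered to the day of the Week 29 visit, 56 days after the last depot injection. The scheduled AE contacts in Table 4 (calls in Weeks 26 to 28 and the Week 29 visit) all fall on or before that day, and the remaining 14 days contain no scheduled contact. This stands, and it makes the practical loss small under that reading.
- **Protocol 9.7 does not set an AE risk period.** It concerns receptor dissociation and opioid analgesia. For the weekly depot it gives up to 2 weeks, well inside 30 days. This stands. The section is still the protocol's own statement of how long drug effect may persist.
- **The events are not lost.** Protocol 12.4 provides by-subject listings of all safety data. The injection-site and C-SSRS summaries (SAP Tables 14.3.3 and 14.3.4.1 to 14.3.4.3) do not state the cut, and Table 14.3.12 on deaths and hospitalizations is not labelled treatment-emergent. This stands, although listings give no incidence by arm and SAP 10.2 leaves it unclear whether deaths follow the AE rule.
- **The direction of any bias is unknown.** Completers in both arms move to standard care, which may be SL BPN, at Week 25. Control subjects may therefore also be taking buprenorphine, and late events in either arm are confounded by non-study treatment. This stands. It argues for showing the follow-up period separately, not for omitting it.

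None of this answers the missing definition.

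**Conclusion.** The point holds as a reporting gap. SAP 10.2 does not define last dose, and under either reading the TEAE tables stop before AE collection ends for an on-schedule completer: 41 collected days untabulated if it means the injection, 14 if it means the later of tablet and injection. Against an assumed 60-day depot period, about 31 or about 4 of those days fall while depot drug may still be present (27 to 32, or 0 to 5, for 56 to 61 days). The large depot gap needs either the injection-only reading or a subject who stops tablets soon after a q4w injection and remains in follow-up.

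Late events may be understated in the CAM2038 tables. The documents establish neither the direction nor the size of such an effect, and they do not show that safety data are lost. The figures rest on an on-schedule calendar, a last tablet on about Day 168, and 2 months taken as 60 days.

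**What to change.** In SAP 10.2, before unblinding:

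1. Keep the start of treatment emergence at randomization.
2. Define last dose as the later of the last tablet and the last injection, counting supplemental injections.
3. Tabulate all TEAEs, SAEs and deaths by arm to the end of protocol AE collection, in two columns: on treatment, and follow-up after last dose. Footnote the follow-up column to say that depot drug may still be present and that standard care has started for completers.
4. State when AE collection ends for early terminators, since Protocol 8.3 and 10.4.1.1 can be read differently.

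For an on-schedule completer this adds 41 days (Days 171 to 211) or 14 days (Days 198 to 211) to the tables, depending on which reading would otherwise have been programmed. The cost is SAP wording and extra table columns. No new data, visits or subjects are needed. The drawback is that the added events are partly confounded by standard care, which is why the periods should be shown apart. This is a cheap improvement.
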